## List of Abbreviations and Definitions

AE	Adverse event
Cavg	Average concentration
Cmax	Maximum concentration
CRF	Case report form
DHEA	Dehydroepiandrosterone
dL	Deciliter
ECG	Electrocardiogram
FSH	Follicle-stimulating hormone
GCP	Good Clinical Practice
GnRH	Gonadotrophin releasing hormone
g	Grams
hCG	Human chorionic gonadotrophin
ICH	International Conference on Harmonization
IGF-1	Insulin-like growth factor-1
IRB	Institutional Review Board
IND	Investigational new drug
IUD	Intra-uterine device
kg	Kilogram(s)
LD50	Median lethal dose
LH	Luteinizing hormone
LOCF	Last observation carried forward
LSC	Least Significant Change
m	Meters
MBL	Menstrual Blood Loss
mg	Milligram(s)
mL	Milliliter
ng	Nanograms
OC	Oral Contraceptive
ODI	Off-Drug Interval
PBAC	Pictorial Blood Loss Assessment Chart
PCOS	Polycystic Ovarian Syndrome
PK	Pharmacokinetic
RBC	Red blood cell
SAE	Serious adverse event
UFSQOL	Uterine Fibroid Symptom Quality of Life Survey
UFS-SSS	Uterine Fibroid Symptom Quality of Life Survey Symptom Severity Score (first 8 questions)
WBC	White blood cell

## 1. INTRODUCTION/BACKGROUND

This statistical analysis plan (SAP) describes the data analysis specifications for study ZPV-201, entitled “A Phase 2, Multi-Center, Parallel Design, Randomized, Double-Blind Study to Evaluate the Safety and Efficacy of 6 and 12 mg Proellex® (Telapristone Acetate) Administered Vaginally in the Treatment of Premenopausal Women with Confirmed Symptomatic Uterine Fibroids”. The preparation of this version of the SAP adheres to Amendment 4 of the ZPV-201 protocol.

## 2. STUDY OBJECTIVES

The purpose of this study is to determine the safety and efficacy of two doses of Proellex compared to placebo in premenopausal women with symptomatic (menorrhagia) uterine fibroids confirmed by MRI.

## 3. STUDY DESIGN

### 3.1 OVERVIEW AND LENGTH OF STUDY

ZPV-201 is a phase 2 3-arm study with two 18-week dosing courses. The study will be conducted in 2 stages, with total study participation being approximately 18 months.

[figure not shown]
In the first stage, women will undergo a baseline assessment period with no treatment, until 15-20 days after the start of their second complete menstrual event. During this phase a pictorial blood loss assessment chart (PBAC) will be utilized as well as sanitary products collected from their first menstrual event, for alkaline hematin assay, to determine menstrual blood loss and confirm eligibility.

In the second stage, subjects will be randomized into one of 3 arms in a 1-1-1 fashion and receive two 18-week courses of treatment at their randomized dose level (6 mg, 12 mg, or placebo), separated by an off-drug interval (ODI). The start of the first 18-week course of treatment (Course 1) should commence 15-20 days after the start of their previous menses. Subjects should be instructed to continue vaginal dosing during their menses throughout the study and not to have sex or insert anything in the vagina for at least 1 hour after the capsule is inserted. Once dosing for Course 1 has stopped, subjects will be followed until menses return. The start of the second 18 week course of treatment (Course 2) will commence 15-20 days after the start of their menses following withdrawal of drug after Course 1 has been completed.

Efficacy will be assessed by: amenorrhea, PBAC scores, uterine fibroid symptoms-symptom severity score questionnaire (UFS-SSS), uterine fibroid volume, uterine volume, [REDACTED]

### **3.2 SAMPLE SIZE CALCULATION/JUSTIFICATION**

Up to 50 female subjects, 15 per dose arm, meeting the inclusion/exclusion criteria will be randomized in a 1-1-1 fashion with the expectation that approximately 45 will be fully eligible for efficacy analyses. The primary endpoint is amenorrhea (no vaginal bleeding intensity > 1). A

## **4. ANALYSIS SETS**

### **4.1 INTENT-TO-TREAT POPULATION**

[figure not shown]
The Intent-to-Treat (ITT) population will consist of all patients who are randomized and who receive study drug.

### **4.2 SAFETY POPULATION**

The Safety population will consist of all patients who are randomized, who receive study drug, and who have some post-baseline assessment of safety data.

## **5. ENDPOINTS**

Efficacy endpoints will be:

- Percentage of subjects who become amenorrheic
  - Percentage change in PBAC scores
  - Percentage change in total and individual UFS-SSS scores
  - Percentage change in size of uterine fibroids as assessed by MRI
  - Percentage change in uterine volume as assessed by MRI
- 

## **6. STATISTICAL METHODOLOGY AND ANALYSES**

### **6.1 GENERAL CONSIDERATIONS**

Standard statistical methods will be employed to analyze all data. It is anticipated that the following techniques may be used: t-test, ANOVA, chi-square test, Fisher's exact test, McNemar's/Bowker's test. Assumptions of normality will be tested using the Shapiro-Wilk test. If distributional assumptions are violated, non-parametric techniques, such as the Wilcoxon signed-rank test, Wilcoxon rank-sum test, and Kruskal-Wallis test, will be employed. Summaries for quantitative variables will include the sample size, mean, median, standard deviation, minimum, and maximum. Summaries for categorical variables will include the number and percent of patients for each outcome.

A last observation carried forward will be used to impute missing data for efficacy variables in the form of a "last observation on treatment".

Statistical significance will be declared if the two-sided p-value is  $\leq 0.05$ .

Additional statistical analyses, other than those described in this SAP, may be performed if deemed appropriate.

### **6.2 INTERIM ANALYSES AND FINAL ANALYSES**

Two sets of analyses will be performed. The first analyses (efficacy endpoints only) will be performed after all subjects complete the first cycle of treatment, and to prevent unblinding, all clinical research and site staff will remain blinded at the subject-level. The second analyses (all endpoints) will be performed after all subjects are finished participating in the study.

### **6.3 ADJUSTMENT FOR MULTIPLE COMPARISONS**

No adjustments for multiple comparisons will be made in this study.

### **6.4 EXTENT OF EXPOSURE**

The duration of exposure will be calculated for each subject. Summary statistics will be presented for each treatment group using the Intent-to-Treat population.

### **6.5 SUBJECT DISPOSITION**

Subject disposition will be summarized in terms of the number of subjects who completed the study and discontinued early from the study. Disposition will be summarized for each treatment group using the Intent-to-Treat population.

### **6.6 DEVIATIONS**

The total number of each deviation type will be summarized for the Intent-to-Treat population.

## **6.7 DEMOGRAPHIC AND BASELINE CHARACTERISTICS**

[figure not shown]
Demographic and baseline characteristics will be summarized for the Intent-to-Treat population. Demographic and baseline data will be listed for all subjects to supplement summary results. Results will be presented for each treatment group.

## **6.8 EFFICACY ANALYSES**

The efficacy analyses will be conducted using the Intent-to-Treat population, as defined in Section 4.1.

### **6.8.1 Amenorrhea**

The proportion of subjects who become amenorrheic will be summarized for each treatment group. Treatment groups will be compared using a chi-square or Fisher's exact test, as appropriate.

[figure not shown]

[figure not shown]
A subject will be considered amenorrheic if they have no bleeding intensity score greater than 1 during a given interval.

The time to amenorrhea in each treatment course will be determined for each subject. This will be calculated as the difference in days between the last bleeding day during a treatment course and the start of treatment in that course. If a subject did not become amenorrheic by the time they reached their last 28 days on-drug during a treatment course then they will be censored. If a subject never experienced a bleeding day after starting treatment in a particular course then they will have their time to event set to 0 days for that course. Other variables may also be examined to determine if they affect time to amenorrhea.

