Study Design and Duration of Treatment:	
This study is a phase 2 3-arm-study with two 18-week dosing courses. The study will be conducted in two stages.
 
In the first stage, women will undergo a baseline assessment period with no treatment, until 15-20 days after the start of their second complete menstrual event. During this phase a pictorial blood loss assessment chart will be utilized as well as sanitary products collected from their first menstrual event, for alkaline hematin assay, to determine menstrual blood loss and confirm eligibility.
 
In the second stage, subjects will be randomized into one of 3 arms in a 1-1-1 fashion and receive two 18-week courses of treatment at their randomized dose (6 mg, 12 mg or placebo), separated by an off-drug interval (ODI). The start of the first 18-week course of treatment (Course 1) should commence 15-20 days after the start of their previous menses. Subjects should be instructed to continue vaginal dosing during their menses throughout the study and not to have sex or insert anything in the vagina for at least 1 hour after the capsule is inserted. Once dosing for Course 1 is stopped, subjects will be followed until menses return. The start of the second 18 week course of treatment (Course 2) will commence 15-20 days after the start of their menses following withdrawal of drug after Course 1 has been completed. During the ODI, subjects will continue to record study information in the daily paper diary and PBAC charts as well as collect sanitary products for alkaline hematin assay.
 
After completion of stage 2 dosing (Courses 1 and 2), subjects will be followed through the subsequent 6 menses (recovery menses plus an additional 5 menstrual events), the subject may be offered the opportunity to enroll in an open-label extension study. Subjects who fail to achieve amenorrhea may enroll in the extension study at Visit 19. Amenorrhea is defined as any 28-day period during treatment (not including the ODIs) without a bleeding score >1. Throughout the study women will record study information in the diary, PBAC, and questionnaires as outlined in the study procedures.
 
Subjects will collect and return used sanitary materials for alkaline hematin assay for their first menstrual event during screening, for the recovery menses menses following Course 1, for the 28 days leading

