12.2.2.1 Primary Endpoint: Incidence of Amenorrhea

The percentage of subjects who become amenorrheic during the 28 days leading up to the last day of dosing at Week 18 will be compared by Chi-Square test. Amenorrhea after a second course of treatment will be analyzed as a secondary endpoint. Testing will evaluate the pooled Proellex doses compared to placebo, each Proellex dose compared to Placebo as well as compare the active dose groups. A Fisher's Exact test will be utilized if the cell sizes are small.

A subject is deemed amenorrheic if they have no bleeding intensity score greater than 1 using the Daily Diary Card in [Appendix 3](#) (spotting not requiring hygiene products) during the 28 day period.

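### SAP 6.8.1 sets time to amenorrhea to 0 days for a woman with no on-drug bleeding day, with no minimum exposure, so a very early stopper can score as an immediate event without the 28 days the protocol requires (minor)

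*SAP*

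**What the plan says.** The SAP version that contains this analysis states: "The preparation of this version of the SAP adheres to Amendment 4 of the ZPV-201 protocol". Section 6.8.1 gives the status rule first: "A subject will be considered amenorrheic if they have no bleeding intensity score greater than 1 during a given interval". It then adds a time to amenorrhea for each course, "calculated as the difference in days between the last bleeding day during a treatment course and the start of treatment in that course".

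Two special cases follow. The first concerns a subject who "did not become amenorrheic by the time they reached their last 28 days on-drug during a treatment course then they will be censored". The second concerns a subject who "never experienced a bleeding day after starting treatment in a particular course then they will have their time to event set to 0 days". The second carries no condition on how long she was treated. SAP 6.8 runs efficacy analyses in the intent-to-treat population, and SAP 4.1 asks only for randomization and receipt of study drug.

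The protocol synopsis, repeated in 8.2.1 and 8.2.3, says: "Amenorrhea is defined as any 28-day period during treatment (not including the ODIs) without a bleeding score >1". Protocol 12.2.2.1 also uses 28 days for the primary endpoint: "The percentage of subjects who become amenorrheic during the 28 days leading up to the last day of dosing at Week 18". The same section describes score 1 as spotting that is compatible with amenorrhea.

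On timing, SAP 3.1 says: "The start of the first 18-week course of treatment (Course 1) should commence 15-20 days after the start of their previous menses". Course 2 has the same 15-20 day offset, counted from the menses that follow withdrawal after Course 1.

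**The concern.** Dosing begins in the second half of a cycle, so every woman has a stretch at the start of a course in which no menses is due. If she stops in that stretch, the absence of bleeding reflects the calendar and says nothing about treatment. Read literally, the 0-day sentence records it as amenorrhea achieved at once. That is the most favorable result the analysis can give, and it goes to a woman who cannot meet the protocol's 28-day definition.

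The rule also separates early stoppers by chance. One who stops just before menses is an event at day 0; one who stops just after the first bleed is not an event. Two programmers could code the short-course case differently, and choosing between the readings after unblinding would be data-dependent.

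**Working it through.** The documents give no target, event count or dropout rate for time to amenorrhea, so there is no figure of the plan's own to reproduce. The check is calendar arithmetic plus applying the rule case by case.

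**Inputs.** Course length 18 weeks (SAP 3.1); first dose 15-20 days after menses onset (SAP 3.1); 15 per arm (SAP 3.2); a 28-day amenorrhea period (protocol synopsis, 8.2.1, 8.2.3, 12.2.2.1). Assumptions: regular cycles, no intermenstrual bleeding, and a cycle length of 28 days. The synopsis uses a nominal 28 days for the PBAC; 24, 32 and 35 days are shown as a range.

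**When the first on-drug menses is due.** Days after first dose = cycle length minus 20, to cycle length minus 15.

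| Cycle (days) | First menses due after first dose |
|---|---|
| 24 | 4 to 9 |
| 28 | 8 to 13 |
| 32 | 12 to 17 |
| 35 | 15 to 20 |

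Every one of these falls before 28 on-drug days, so a 28-day minimum excludes a woman who is merely between menses.

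**The rule applied.** 'As written' follows the 0-day sentence literally and reads a bleeding day as score above 1. 'With minimum' requires 28 on-drug days after the last score above 1, or after the start of treatment if there is none.

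| Case | As written | With minimum |
|---|---|---|
| No bleeding, stops day 7 | event, day 0 | censored, day 7 |
| No bleeding, stops day 27 | event, day 0 | censored, day 27 |
| No bleeding, stops day 28 | event, day 0 | event, day 0 |
| No bleeding, full 126 days | event, day 0 | event, day 0 |
| Score 3 on day 5, stops day 12 | censored | censored, day 12 |

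The conflict is therefore confined to courses shorter than 28 on-drug days. For a woman who completes a course without bleeding, 0 days agrees with the protocol.

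**Weight of one woman.** At day 0 all 15 in the arm are at risk, so each such event adds 1/15 = 6.7 percentage points to the arm's cumulative curve. Two add 2/15 = 13.3 and three add 3/15 = 20.0. Censoring adds none. The counts of one to three are assumed.

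**Bleeding day.** A course is 18 x 7 = 126 days. Counting the first dosing day as 0, it runs to day 125, and the last 28 days are days 98-125. If a bleeding day means score above 1, a completer who is amenorrheic in that window has a time of at most 97. If score-1 spotting counts, her time can fall anywhere in 98-125. For example, spotting on day 120 as the only entry gives 0 on the first reading and 120 on the second.

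**The case against.** The best defense is to read the sentences in order. The censoring rule comes first, and under the 28-day definition a woman who stops on day 8 never became amenorrheic, so she is already censored. The 0-day sentence then only fills a gap in the formula, which has no last bleeding day for a woman who never bled. That may well be the intent. But the censoring sentence refers to reaching the last 28 days on drug and does not say what happens when there were fewer than 28. The 0-day sentence is unqualified. The ambiguity stands.

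The objection that little depends on it is sound. Time to amenorrhea is not among the protocol's primary or secondary endpoints or in the SAP section 5 list, it is absent from the SAP version written to Amendment 3, and the visible text names no between-arm test for it.

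On bleeding day, the objection is largely right. The status sentence just before uses score above 1, so that is very likely what is meant, and figures in 6.8.1 and SAP Appendix 1 are not shown and may define it. A reader should not infer that the SAP counts spotting; this is a wording clarification.

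A reader might also infer from the last-observation-carried-forward rules in SAP 6.1 and Protocol 12.3 that early stoppers are credited as amenorrheic in the primary proportion. The readable text does not show that: Protocol 12.2.2.1 fixes a 28-day window ending with the last Week 18 dose, and the SAP's interval text is not visible.

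**Conclusion.** The point holds as a minor defect in a supplementary analysis. The 0-day sentence lacks an exposure condition, and the timing of dosing means a woman on any arm, placebo included, can trigger it by stopping before about day 8-13 (28-day cycle, no intermenstrual bleeding, both assumed). Each such woman moves her arm by 6.7 points at day 0.

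It would be tempting to conclude that the rule favors active treatment. The documents do not support this: no early-stopping rate is given for any arm, and which way the comparison moves depends on how early stopping is distributed between arms. Size and direction are unknown. On the visible text the primary amenorrhea proportion is not affected.

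**What to change.** In SAP 6.8.1, count a time-to-amenorrhea event, including one at 0 days, only if at least 28 on-drug days follow the last day with a score above 1, or follow the start of treatment if there is no such day. Otherwise censor at the last on-drug diary day. In the same sentence, say that a bleeding day means score above 1, unless the text not shown already does.

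This keeps the SAP's existing approach, which rests on the last bleeding day and the last 28 days on drug. It is not identical to the protocol's wording of any 28-day period: a woman with an earlier clear 28 days who bleeds again in her last 28 days meets that wording but stays censored. The SAP should say so.

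The cost is two or three sentences and no new data. The downside is that a few early stoppers move from event to censored. The change should be made before unblinding. Nothing in this point calls for changes to the primary analysis or to the missing-data rules.

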#### **6.8.2 PBAC**

Total PBAC scores will be determined from daily PBAC entries grouped into the following 28 day intervals:

Total PBAC scores and percentage change from baseline in Total PBAC scores will be summarized for each treatment group. Pairwise comparisons between treatment groups will be performed using t-tests and Wilcoxon rank-sum tests, as appropriate. Statistical significance of the change from baseline within treatment groups will be determined using a paired t-test or Wilcoxon signed-rank test, as appropriate.

### 6.8.3 UFS-SSS

The individual and combined symptom severity scores and percentage change from baseline will be summarized at the end of course 1 treatment, course 2 treatment, and each follow-up visit. Pairwise comparisons between treatment groups will be performed using t-tests and Wilcoxon rank-sum tests, as appropriate. Statistical significance of the change from baseline within treatment groups will be determined using a paired t-test or Wilcoxon signed-rank test, as appropriate.

[figure not shown]
### 6.8.4 Uterine Fibroids

[figure not shown]
Uterine fibroid volume (by prolate ellipsoid method) will be determined by MRI. [REDACTED]

Total fibroid volume and percentage change in total fibroid volume will be summarized. Pairwise comparisons between groups will be performed using t-tests and Wilcoxon rank-sum tests, as appropriate. Statistical significance of the change from baseline within treatment groups will be determined using a paired t-test or Wilcoxon signed-rank test, as appropriate.

### 6.8.5 Uterine Volume

Uterine volume (assessed by MRI) and the percentage change in uterine volume will be summarized. Pairwise comparisons between groups will be performed using t-tests and Wilcoxon rank-sum tests, as appropriate. Statistical significance of the change from baseline within treatment groups will be determined using a paired t-test or Wilcoxon signed-rank test, as appropriate.

## **6.9 SAFETY ANALYSES**

The safety analyses will be conducted using the Safety population, as defined in Section 4.2.

### **6.9.1 Adverse Events (AEs)**

[figure not shown]
Treatment-emergent AEs (TEAEs) are defined as those AEs with an onset date and time equal to or after the start of study medication, or those events in which the onset date and time are before the start of study medication but worsened after the start of study medication. To be conservative, in the case of a missing onset time for an AE, an AE with a start date equal to or after the dosing date will be considered treatment-emergent. AE's with missing onset dates will also be considered treatment-emergent.

[figure not shown]
All TEAEs will be summarized by treatment group. The number of TEAEs as well as the number and percentage of subjects who experienced at least one TEAE will be summarized for each system organ class and each preferred term. The percentage will be based on the number of subjects in a particular treatment group included in the Safety population. Each subject will contribute at most one count per summarization category. TEAEs potentially related to study medication, serious TEAEs, and TEAEs leading to withdrawal will be summarized in a similar manner.

If a subject has more than one AE that codes to the same preferred term, the subject will be counted only once for that preferred term. Similarly, if a subject has more than one AE within a system organ class category, the subject will be counted only once for that system organ class category.

TEAEs will also be summarized by maximum severity and by strongest relationship to treatment within each treatment group. Serious adverse events (SAEs) will be tabulated and listed in a

manner similar to TEAEs. A listing of all AE data will be provided to supplement the tabulated results.

**Repros Therapeutics Inc.  
[name]  
[name]**

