8.2 Study Design

8.2.1 Overview of Study Design

This study is a phase 2 3-arm-study with a 36 week active dosing period. The study will be conducted in two stages.

[figure not shown]
[figure not shown]
[figure not shown]
In the first stage, women will undergo a baseline assessment period, with no treatment, until 15-20 days after the start of their second complete menstrual event. During this phase a pictorial blood loss assessment chart and daily diaries will be utilized. Used sanitary products from the first menstrual event will be collected and returned to the clinic for alkaline hematin assay. This assay will confirm subject eligibility (MBL must be 80 mL or greater by alkaline hematin assay for subjects to qualify).

In the second stage, subjects will be randomized into one of 3 arms in a 1-1-1 fashion. The start of the 18 week dosing period (Course 1) in this stage of the study should commence 15-20 days after the start of their first menses after Visit 2. Once active dosing is stopped, subjects will be followed until menses returns. The start of the second 18 week dosing period (Course 2) will commence 15-20 days after the start of their menses following withdrawal of drug after Course 1 has been completed. During the non dosing off-drug interval (ODI), subjects will continue to record study information in the daily paper diary and PBAC charts.

After end of dosing in Course 2, subjects will be followed through the subsequent recovery menses and for an additional 5 menstrual events, after which the subject may be offered the opportunity to enroll in an extension study. Subjects who fail to achieve amenorrhea may enroll in the extension study at Visit 19. Amenorrhea is defined as any 28-day period during treatment (not including the ODIs) without a bleeding score >1. Throughout the study women will record study information in the diary, PBAC and questionnaires as outlined in the study procedures.

In addition to the diary information, endometrial thickness will be recorded at screening and every month thereafter. Assessment of

trough levels of drug will be determined at every office visit during the first and second 18 week dosing periods.

The primary efficacy analysis will be conducted when all subjects complete the first cycle of treatment. A second analysis will summarize the subject's second treatment cycle which will be conducted after all subjects complete study treatment and follow-up.

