8.2.3 Randomization and Blinding

At Visit 3, subjects will be randomized to treatment in Arms 1, 2, or 3. Subjects will be treated with one capsule daily of 6 mg or 12 mg of Proellex, or placebo, which will be administered for a total of 36 weeks (two 18 week courses separated by an ODI) before the 6 cycle follow up is started. After the second treatment course is completed the subjects will be followed for 6 menstrual events to determine durability of effect of treatment, after which they may be offered the opportunity to enroll in an open-label extension study. Subjects who fail to achieve amenorrhea may enroll in the extension study at Visit 19. Amenorrhea is defined as any 28-day period during treatment (not including the ODIs) without a bleeding score >1. Each treatment course will be separated by an ODI. Blinded treatments kits will be randomized and distributed by the packaging company.

For the statistical analysis at the end of the first course of treatment, only statistical staff will be unblinded. All clinical operations staff and staff at investigative sites will remain blinded until completion of the study.

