10. ASSESSMENT OF SAFETY

10.1 Adverse Events

10.1.1 Reporting Adverse Experiences

Any AE (clinical sign, symptom, or disease) temporally associated with the use of this investigational drug, whether or not considered related to the investigational product, shall be documented on the CRF and eDC. All SAEs and AEs reported by the subject or observed by the Principal Investigator for up to 30 days after the last dose of study medication will be individually listed. After Visit 20, all SAEs and any adverse events that the investigator considers to be due to the study drug (e.g. hepatotoxicity) and not those considered to be due to withdrawal of the drug (e.g. vaginal bleeding), will be collected. The signs and symptoms, time of onset (24-hour clock), duration, action taken and follow-up procedures will be reported.

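### SAP 6.9.1 gives treatment-emergent AEs no end date, so serious and drug-related AE percentages could differ between arms through off-drug follow-up length if staying past Visit 19 differs by arm

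*SAP*

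**What the plan says.** SAP 6.9.1 counts as treatment-emergent "those AEs with an onset date and time equal to or after the start of study medication", together with earlier events that worsen after that point. It states no end to the window. It adds that "AE's with missing onset dates will also be considered treatment-emergent". For the denominator, "The percentage will be based on the number of subjects in a particular treatment group included in the Safety population". The same rules feed the tables of all TEAEs, potentially related TEAEs, serious TEAEs, and strongest relationship to treatment.

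Protocol 10.1.1 does not collect AEs evenly over that window. AEs and SAEs "for up to 30 days after the last dose of study medication will be individually listed". Later, the scope narrows: "After Visit 20, all SAEs and any adverse events that the investigator considers to be due to the study drug" are collected, but "not those considered to be due to withdrawal of the drug (e.g. vaginal bleeding), will be collected". Protocol 10.1.3 requires SAEs to be reported until the study is complete, whether or not they look drug-related.

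Follow-up after Course 2 runs through six menses, to Visit 24. The exception is in protocol 8.2.1: "Subjects who fail to achieve amenorrhea may enroll in the extension study at Visit 19". Protocol 8.2.3 and the synopsis repeat it. This exit came with Amendment 4. The SAP that follows Amendment 4 has the same TEAE definition as the SAP that follows Amendment 3.

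**The concern.** A woman who stays to Visit 24 contributes about five more months of off-drug time to the TEAE tables than one who leaves at Visit 19. Whether she may leave early depends on amenorrhea, which is the outcome the drug is meant to change. If the drug works, women on active treatment would tend to stay longer. A simple percentage with the whole arm as denominator takes no account of this.

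Serious events and drug-attributed events are the two kinds still recorded after Visit 20, so the serious and related tables are the most exposed. For non-serious events in that late period, only those judged related are recorded. The related table therefore also picks up a change in collection rule, and the balance of related to unrelated events shifts in women who stay.

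Safety is part of the primary objective (protocol section 7). Readers will compare these tables across arms of about 15 women, where one woman is 1/15 = 6.7 points.

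**Working it through.** The documents give no AE rate, rollover rate or visit calendar, so there is no stated figure to reproduce for this point. The only check available is on the timeline.

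**Inputs from the documents**
- Two 18-week courses: 2 × 126 = 252 days (protocol 8.2.3).
- Course 2 starts 15–20 days after the start of the menses that follow Course 1 (8.2.1).
- Six menses of follow-up after Course 2, ending at Visit 24 (8.2.3, 12.2.2.2).
- Fifteen women per arm (12.1).

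**Assumptions**
- 28-day cycles.
- Visits 19, 20 and 24 fall about 28, 56 and 168 days after the last dose.
- ODI of 29–62 days, that is, menses starting 14–42 days after Course 1 ends, plus 15–20 days.
- AE collection is complete up to Visit 20.

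**Timeline check.** With 10.5 weeks of screening and a 6-week ODI, 10.5 + 18 + 6 + 18 + 24 = 76.5 weeks, or 17.6 months. This agrees with the protocol's approximate 18 months.

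**Length of the TEAE window**
- Leave at Visit 19: (252 + 29 to 62 + 28)/7 = 44.1 to 48.9 weeks.
- Stay to Visit 24: (252 + 29 to 62 + 168)/7 = 64.1 to 68.9 weeks.
- Extra time: 20 weeks, or 41–45%.
- Of this, Visit 20 to Visit 24 is (168 − 56)/7 = 16 weeks of restricted collection.
- Fully captured extra time: 20 − 16 = 4 weeks. 4/48.9 = 8% and 4/44.1 = 9%.

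With a 6-week ODI, a woman who stays has a 66-week window. Of that, (6 + 24)/66 = 45% is off drug, and (24 − 30/7)/66 = 30% lies more than 30 days after the last dose.

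**Illustration of size.** Give every arm the same true event rate λ per year, and let incidence be 1 − exp(−λ × weeks/52). The window is 46 weeks for a leaver and 66 for a stayer. Any gap then comes only from follow-up and collection. For any AE, the rate is assumed to be 1.0 per year up to Visit 20 and 0.1 captured per year after it.

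| Event type, assumed rate | Leaver | Stayer | Gap, 80% vs 20% staying | Gap, 100% vs 0% | Gap, equal staying |
|---|---|---|---|---|---|
| Serious or related, 0.2/yr | 16.2% | 22.4% | 3.7 points | 6.2 points | 0 |
| Serious or related, 0.5/yr | 35.7% | 47.0% | 6.7 points | 11.2 points | 0 |
| Any AE, 1.0/yr | 58.7% | 62.9% | 2.5 points | 4.2 points | 0 |

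Example, row 1: 1 − exp(−0.2 × 46/52) = 0.162 and 1 − exp(−0.2 × 66/52) = 0.224. The full gap is 0.062, and with 80% against 20% staying it is 0.6 × 0.062 = 0.037.

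In arms of 15, the serious or related gaps equal 0.037 × 15 = 0.6 to 0.112 × 15 = 1.7 women. The any-AE gaps equal 0.4 to 0.6 women.

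**With a cutoff at last dose + 30 days**, the window is 42 + 30/7 = 46.3 weeks. Incidence is 16.3% at 0.2/yr and 35.9% at 0.5/yr. A woman leaving at day 28 loses two days of that window, which changes these figures by no more than 0.2 points. The gap all but disappears.

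**The case against.** Several stronger readings are tempting, and the documents do not support them.

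- **That the rule builds in a difference between arms.** It does so only if staying past Visit 19 differs by arm. No document gives an amenorrhea, rollover or AE rate, and rollover is optional. The exit is open only to women with no qualifying 28-day period at any time during treatment. That is a narrower group than those who fail the primary endpoint, which looks only at the last 28 days of Course 1. That leavers would be mostly on placebo is plausible but not established.
- **That late events are recorded only if judged drug-related.** This is wrong for SAEs, which are collected whatever their cause, and transaminases above 3 × ULN are reported as SAEs (protocol 10.1.2, 10.1.3). Longer follow-up is all that can move the serious table.
- **That 41–45% more time applies to all AEs.** Fully captured time rises by only 8–9%.
- **That protocol 10.1.1 already sets a 30-day TEAE window.** That sentence governs which events are listed. Collection goes on past it, and the SAP does not use it.

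Other points also stand. A constant event rate off drug is a weak assumption for related events, which would be expected to fall after dosing stops. Site staff remain blinded to the end, so late causality judgments are made blind. The AE tables are descriptive, so no type I error is affected. The SAP provides a full AE listing and disposition by arm, from which a reader could pick out late events. An open window is also the inclusive choice, because it keeps late attributed events, such as the protocol's own example of hepatotoxicity, in the main table.

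Parts of SAP 6.9 are withheld, so tables by period cannot be ruled out. The TEAE definition itself is legible and reads as complete, and listings do not substitute for a summary by period.

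**Conclusion.** The point holds as a conditional one. As written, SAP 6.9.1 combines on-drug events with off-drug follow-up whose length can depend on outcome, over a whole-arm denominator. If staying past Visit 19 differs by arm, the serious and related TEAE percentages could differ for that reason alone, and the related table also because of selective collection.

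The size is not derivable from the documents. The 3.7 to 11.2 points for serious or related events are illustrations that rest on 80/20 to 100/0 staying, constant event rates and assumed visit timing. With equal staying the gap is zero. The effect on the all-TEAE table is small, at 2.5 to 4.2 points under the same staying assumptions. The ODI is also off drug, but it applies to every woman who reaches it. It is a labelling matter and not part of the Visit 19 mechanism.

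The point affects how the safety tables are read. It does not affect the efficacy analysis or any test.

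**What to change.** In SAP 6.9.1:

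1. End the main TEAE window at a stated time after the last dose each woman takes. Thirty days is one option, in line with the listing period in protocol 10.1.1.
2. Identify events with onset in the ODI as their own period.
3. Say to which period an event with a missing onset date belongs.
4. Put later events in a separate post-treatment follow-up table, with the women still followed in each arm as denominator. Footnote the collection rule after Visit 20. Because staying may depend on outcome, this table should not be read as a randomized comparison.
5. Keep every event in the listings.

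The cost is SAP wording and one extra table, with no new data. The downside is that late drug-attributed events move from the main table to the follow-up table, where they remain visible.
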